# 7.4 Physician Surgery Questionnaire (PSQ)

For each of the PSQ questions, the number and percentage of subjects in each response category will be summarized at Baseline by treatment group and overall. No statistical tests will be performed.

## 7.5 Reason for Study Participation Questionnaire

Descriptive statistics will be presented for reasons for study participation for each treatment group. No statistical tests will be performed.

# 8.0 Efficacy Analyses

## 8.1 General Considerations

All efficacy analyses will be conducted in the FAS Population.

Unless otherwise specified, during the 12-month placebo-controlled Treatment Period, elagolix plus E2/NETA group will be compared against placebo. Statistical tests will be conducted at an alpha level of 0.05 (two-sided). A test will be deemed significant if the P value rounded to three decimal places is less than or equal to 0.05 unless otherwise specified.

Efficacy endpoints collected during each of the placebo-controlled and open-label Treatment Periods will also be summarized as observed cases (by treatment group); no comparisons or statistical tests will be performed.

The End of 12-Month Placebo-Controlled Treatment Period analyses will be performed after all ongoing subjects have completed the 12-month placebo-controlled Treatment Period and the database has been locked. This will be the only and final analysis for the efficacy endpoints collected in the 12-Month Placebo-Controlled Treatment Period.

Unless otherwise specified, categorical data will be summarized by frequencies and percentages; continuous data will be summarized by the mean, standard deviation, median, minimum, and maximum. For the analyses of change from baseline, the withingroup changes will be summarized with the mean, standard deviation or standard error, and 95% confidence intervals (CIs); between-group differences will be summarized with the mean, standard error, P value (as appropriate), and the 95% CIs.

For efficacy variables, the baseline during the 12-month placebo-controlled Treatment period (Months 1 - 12) will be the last non-missing value obtained prior to or on Study Day 1.

## 8.2 Handling of Missing Data

The primary objective of the study is to evaluate the long-term safety and tolerability of Elagolix plus E2/NETA. The efficacy analyses will be based on the observed data. The missing data will not be replaced or imputed. Potential impact due to COVID-19 will be recorded in the database. Listings will be provided to summarize AE and death related to COVID-19 infection, COVID-19 impacted visits, COVID-19 related study drug interruptions, COVID-19 status, and COVID-19 supplemental signs/symptoms.

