#### **Pharmacokinetic and Statistical Abbreviations**

ANOVA Analysis of variance
ANCOVA Analysis of covariance

MMRM Mixed-model with repeated measures

PD Pharmacodynamic PK Pharmacokinetic

SAP Statistical Analysis Plan

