#### **UFS-QoL**

Improvement in quality of life will be assessed on the UFS-QoL Questionnaire (4-week recall). The change from baseline to each scheduled assessment will be calculated and summarized for each of the UFS-QoL subscales (symptom severity, concern, activities, energy/mood, control, self-conscious and sexual function) and the Health Related Quality of Life Questionnaire (HRQoL) total. The change from Baseline to Month 6 and Month 12 during the double-blind Treatment Period will be analyzed using ANCOVA with treatment as the main effect and corresponding Baseline UFS-QoL as a covariate to compare the elagolix dose group to placebo.

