## 3.3 Other Efficacy Endpoints

Other efficacy endpoints include the following:

- PGIC for Menstrual Bleeding Symptom at Month 3, Month 6, Month 9 and Month 12;
- Change from baseline for the UFS-QoL at Month 6 and Month 12.

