## 8.5.2 Uterine Fibroid Symptoms Quality of Life (UFS-QoL)

Improvement in quality of life will be assessed on the UFS-QoL Questionnaire (4-week recall). Each of the UFS-QoL subscales (symptom severity, concern, activities, energy/mood, control, self-conscious, and sexual function) and the HRQL total at

Month 6, Month 12, Month 18, Month 24, Month 30, Month 36, Month 42, Month 48, and Final Visit during the Treatment Period will be calculated and summarized by treatment group. The change from Baseline to Month 6, Month 12, and Final Visit during the placebo-controlled Treatment Period will be analyzed using ANCOVA with treatment as the main effect and corresponding Baseline UFS-QoL as a covariate to compare elagolix dose group to placebo.

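### The Month 12 UFS-QoL test ignores women who have only a Month 6 score; an MMRM would use them and would protect against bias if dropout follows early response

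*SAP*

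**What the plan says.** SAP 3.3 lists "Change from baseline for the UFS-QoL at Month 6 and Month 12" among the other efficacy endpoints. SAP 8.5.2 plans the test: "The change from Baseline to Month 6, Month 12, and Final Visit during the placebo-controlled Treatment Period will be analyzed using ANCOVA". The model is "ANCOVA with treatment as the main effect and corresponding Baseline UFS-QoL as a covariate", so the Month 6 score does not enter the Month 12 model. Protocol 8.1.6.2 has the same method without Final Visit: "The change from Baseline to Month 6 and Month 12 during the double-blind Treatment Period will be analyzed using ANCOVA". SAP 8.2 adds "The efficacy analyses will be based on the observed data" and "The missing data will not be replaced or imputed".

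In the Year 1 table of Protocol Appendix C, UFS-QoL is scheduled at Day 1, Month 6, Month 12 and the Premature Discontinuation visit. The Post-Treatment Follow-Up table has no UFS-QoL. The SAP does not define Final Visit and gives no rule for placing a discontinuation score at a scheduled visit.

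SAP 8.1 sets two-sided tests at 0.05 with 95% confidence intervals for between-group differences. SAP 3.1, 3.2 and 10.0 define no primary or secondary efficacy endpoint.

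**The concern.** The Month 12 ANCOVA compares women still assessed at Month 12. SAP 4.0 defines the full analysis set to include women who do not finish, but those without a Month 12 score drop out of this test, although their Month 6 score says something about what Month 12 would have been.

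That matters if leaving is linked to response. Protocol 5.4 withdraws a woman who needs surgery for fibroids and bleeding during treatment, or a transfusion for heavy bleeding after 28 days of study drug. Protocol 5.2.3.5 discontinues a woman prescribed tranexamic acid. Each event reflects poor symptom control, so each is plausibly commoner on placebo. The placebo mean at Month 12 would then come from women who were doing better, and the treatment difference would shrink. At stake are the estimate and interval coverage for the plan's tested quality-of-life results, not a safety conclusion.

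**Working it through.** **Plan figures.** There is no power calculation to reproduce: 500 women were chosen by clinical review (Protocol 8.2, SAP 2.4). A 2:1 split of 500 is 333.3 and 166.7, which agrees with both 335/165 (protocol) and 333/167 (SAP).

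**Attrition.** The only retention figure is about 50 of 500 completing 48 months, or 10%. If the dropout hazard were constant (assumption):

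- dropout by Month 12 = 1 − 0.10^(12/48) = 1 − 0.562 = 44%;
- dropout between Months 6 and 12, among women still present at Month 6 = 1 − 0.10^(6/48) = 1 − 0.750 = 25%.

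Actual 12-month dropout could be much lower, so a range is used.

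**Mechanism.** Let ρ be the correlation of Month 6 and Month 12 changes given treatment and baseline. Let m be the mean Month 6 residual among women who stay, in each arm. Then

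bias of the Month 12 ANCOVA ≈ ρ × (m active − m placebo).

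Equal selection in both arms cancels. Stronger loss of poor responders on placebo makes the bias negative.

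**Simulation.** All inputs here are assumed. There are 335 and 165 women and 1,500 to 3,000 replicates per scenario. Change = effect × treatment + 0.4 × baseline + √0.84 × residual, so its SD is √(0.16 + 0.84) = 1. Every woman has a Month 6 score. Where dropout is response-driven, its log-odds fall by 1 per SD of better Month 6 change. In the placebo-only rows, active-arm dropout is random at the same rate. Bias is in SD units.

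| Dropout after Month 6 | Effect | ρ | Active / placebo dropout | ANCOVA bias | ANCOVA 95% CI coverage | MMRM bias |
|---|---|---|---|---|---|---|
| Unrelated to response | 0.8 | 0.6 | 25% / 25% | −0.005 | 95.5% | −0.005 |
| Same rule, no effect | 0 | 0.6 | 30% / 30% | 0.000 | 94.8% | 0.000 |
| Same slope, equal rates | 0.8 | 0.6 | 25% / 25% | 0.002 | 95.4% | 0.001 |
| Same rule | 0.8 | 0.6 | 18% / 30% | −0.048 | 92.1% | 0.002 |
| Same rule | 0.8 | 0.6 | 30% / 46% | −0.067 | 90.4% | −0.002 |
| Same rule | 1.2 | 0.6 | 24% / 46% | −0.092 | 87.2% | 0.000 |
| Placebo only | 0.8 | 0.6 | 10% / 10% | −0.048 | 91.8% | −0.003 |
| Placebo only | 0.8 | 0.4 | 25% / 25% | −0.073 | 89.2% | −0.001 |
| Placebo only | 0.8 | 0.6 | 25% / 25% | −0.111 | 81.0% | −0.003 |
| Placebo only | 0.8 | 0.8 | 25% / 25% | −0.146 | 68.7% | −0.001 |
| Placebo only | 0.8 | 0.6 | 44% / 44% | −0.180 | 64.7% | 0.003 |
| Placebo only, no effect | 0 | 0.6 | 25% / 25% | −0.110 | 81.4% | −0.002 |

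**Check against the formula.** In the three 25% placebo-only rows with effect 0.8, bias divided by ρ should be constant: 0.073/0.4 = 0.183, 0.111/0.6 = 0.185, 0.146/0.8 = 0.183. It is.

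**As a share of the effect.** Same rule: 0.048/0.8 = 6%, 0.067/0.8 = 8%, 0.092/1.2 = 8%. Placebo only at ρ = 0.6: 0.048/0.8 = 6% to 0.180/0.8 = 23%.

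**Precision.** If dropout is random at rate p in both arms, the variance ratio of MMRM to observed-case ANCOVA is about 1 − pρ². With p = 0.25 and ρ = 0.6 this is 1 − 0.25 × 0.36 = 0.91, so the standard error is about 5% smaller (√0.91 = 0.954). The MMRM loses nothing when there is no bias to remove.

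**The case against.** **Incentives also run the other way.** Every placebo woman who completes Month 12 moves to active treatment, which is a reason to stay. The BMD discontinuation rules remove women regardless of bleeding response, plausibly more often from the active arm. This stands: the documents make response-linked, unequal dropout plausible but do not establish it.

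**Early leavers are not lost to all testing.** Women who leave after Month 6 still enter the Month 6 ANCOVA, a discontinuation score is scheduled, and Final Visit presumably includes them. This also stands. A reader might infer that Final Visit simply carries the Month 6 score forward, but the SAP does not say so, and the last score could be the one taken at exit. Final Visit still does not replace a Month 12 estimate. Read as the last of the Month 6 and Month 12 scores, it differed from the true Month 12 effect by +0.052 SD in the 25% placebo-only case (effect 0.8, ρ = 0.6), and by +0.131 SD when the effect waned from 0.8 to 0.5 SD.

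**The MMRM's success is partly built in.** The simulation lets dropout depend only on the observed Month 6 score, which is the condition under which an MMRM is unbiased. A woman who deteriorates after Month 6 and then has surgery need not fit it. This stands as a limit on the fix.

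**No decision would change.** In the largest case, 0.8 − 0.18 = 0.62 SD. With 44% missing, about 188 and 92 women remain, the standard error is about 0.917 × √(1/188 + 1/92) = 0.117, and z = 0.62/0.117 = 5.3. For a large effect the test survives. What suffers is the estimate and its interval, and scales with smaller effects have less room.

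**The abbreviation.** The protocol lists "MMRM Mixed-model with repeated measures" among its abbreviations. A reader might infer that a promised analysis was dropped. Neither document assigns that model to any analysis, so the entry supports no such conclusion.

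**Conclusion.** The point holds in conditional form. The plan's Month 12 test does not use the Month 6 scores of women who have no Month 12 score. If dropout depends on early response and differs by arm, the Month 12 difference can be biased, most likely against the active treatment. Under assumed effects of 0.8 to 1.2 SD, correlations of 0.4 to 0.8 and dropout of 10% to 46%, the bias ranges from 0 to about 0.18 SD. It is zero if dropout is unrelated to response, if one rule acts in both arms with no treatment effect, or if selection and dropout rates match.

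A reader might go further and conclude that the planned comparison is biased, or attach a single percentage to the shortfall. The documents support neither: they give no 12-month dropout rate, SD, effect size or correlation, and the share of the effect moved from 0% to 23% across the scenarios with an effect.

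The planned ANCOVA is not an error, and protocol and SAP agree on it at Months 6 and 12. A better method is available at little cost for an other efficacy endpoint in a safety study. Severity is low.

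**What to change.** In SAP 8.5.2:

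- For each UFS-QoL scale, make the Month 6 and Month 12 comparison one MMRM with treatment, visit, treatment-by-visit, baseline and baseline-by-visit, and an unstructured covariance. Report the treatment difference at each visit.
- State how a score from the Premature Discontinuation visit is assigned to a scheduled visit.
- Define Final Visit.
- Keep the observed-case and Final Visit ANCOVAs as supportive.

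The no-imputation statement in SAP 8.2 can stay, since an MMRM also uses observed data. If the Month 12 lock has already passed, report the MMRM as a labelled sensitivity analysis.

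The cost is SAP wording and slightly more analysis work, with no new data. The downside is reliance on a missing-at-random assumption. The model also gains nothing from a woman who left before Month 6 unless her discontinuation score is assigned to a visit.

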## 8.3 Primary Efficacy Endpoint and Analyses

As the objective of this study is to evaluate the long-term safety and tolerability of elagolix 300 mg BID with E2/NETA, no primary efficacy endpoint is defined.

## 8.4 Secondary Efficacy Endpoint and Analyses

As the objective of this study is to evaluate the long-term safety and tolerability of elagolix 300 mg BID with E2/NETA, no secondary efficacy endpoint is defined.

## 8.5 Other Efficacy Endpoints and Analyses

Other efficacy assessments include the following:

- PGIC for Menstrual Bleeding Symptom;
- Change from baseline for the UFS-QoL.

## 8.5.1 Patient Global Impression of Change (PGIC)

For PGIC on menstrual bleeding (PGIC – MB), the number and percentage of subjects in each response category will be summarized at Month 3, Month 6, Month 9, Month 12 and Final Visit during the placebo-controlled double-blind 12-month Treatment Period by treatment group.

The response categories of "Very Much Improved" and "Much Improved" will be combined together. The remaining five categories of the PGIC scale will be combined and labeled "Otherwise." The number and percentage of subjects with response of (a) "Very Much Improved" or "Much Improved," and (b) "Otherwise" will be summarized at Month 3, Month 6, Month 9, Month 12 and Final Visit during the placebo-controlled Treatment Period by treatment group. Comparisons will be made using a Miettinen– Nurminen (M-N) test [1] for Month 3, Month 6, Month 9, Month 12, and Final Visit assessments in placebo-controlled Treatment Period. The p-value of the Miettinen-Nurminen test will be reported.

## 8.5.2 Uterine Fibroid Symptoms Quality of Life (UFS-QoL)

Improvement in quality of life will be assessed on the UFS-QoL Questionnaire (4-week recall). Each of the UFS-QoL subscales (symptom severity, concern, activities, energy/mood, control, self-conscious, and sexual function) and the HRQL total at

Month 6, Month 12, Month 18, Month 24, Month 30, Month 36, Month 42, Month 48, and Final Visit during the Treatment Period will be calculated and summarized by treatment group. The change from Baseline to Month 6, Month 12, and Final Visit during the placebo-controlled Treatment Period will be analyzed using ANCOVA with treatment as the main effect and corresponding Baseline UFS-QoL as a covariate to compare elagolix dose group to placebo.

# 9.0 Safety Analyses

# 9.1 General Considerations

Safety summaries will be provided separately using the Safety Analysis Set during the placebo-controlled Treatment Period, Safety Analysis Set during the open-label Treatment Period, and All Elagolix plus E2/NETA Analysis Set as defined in Section 4.0. Unless otherwise specified, no statistical comparisons or tests will be performed on Safety Analysis Set during the open-label Treatment Period or the All Elagolix plus E2/NETA Analysis Set.

Unless otherwise specified, the baseline for the 12-month placebo-controlled Treatment Period will be the last non-missing value obtained prior to or on Study Day 1. The baseline during the open-label Treatment Period will be the last non-missing value obtained prior to or on the initiation day of elagolix plus E2/NETA. The baseline for All Elagolix plus E2/NETA Analysis Set will be the last non-missing value obtained prior to or on the initiation day of elagolix plus E2/NETA.

All safety analyses will be based on observed data. Unless otherwise specified, missing data will not be imputed. The COVID-19 pandemic has interfered with the conduct of this study. Potential impacts due to COVID-19 are recorded in the database. Listings will be provided to summarize AE and death related to COVID-19 infection, COVID-19 impacted visits, COVID-19 related study drug interruptions, COVID-19 status, and COVID-19 supplemental signs/symptoms.

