#### **Definition of Terms**

Washout Period The minimum interval of time for washout of hormonal therapy

(if applicable) or other prohibited medications (if applicable).

Screening Period The approximately 2.5 to 5 month period prior to

randomization on Day 1, when screening procedures are performed to establish eligibility. Subjects may either enter the Screening Period directly, if no washout is required, or enter

after completing the Washout Period (if applicable).

Day 1 (Randomization) or Treatment

Period Day 1

The day a subject takes her first dose of study drug. Day 1 will occur between the first and tenth day of the onset (first day with

full menstrual flow) of menses.

Month A month is defined as 28 days.

Product Collection Visits (PCVs) Visits at which subjects return used sanitary products for

assessment of alkaline hematin levels (during screening); visits should occur within approximately 5 days after the last sanitary product was collected during a bleeding and/or spotting

product was collected during a bleeding and/or spotting

episode.

Heavy Menstrual Bleeding Menorrhagia or > 80 mL blood loss

2.0	Table of Contents	
1.0	Title Page	1
1.1	Protocol Amendment: Summary of Changes	2
1.2	Synopsis	
1.3	List of Abbreviations and Definition of Terms	
2.0	Table of Contents	14
3.0	Introduction	19
3.1	Uterine Fibroids	19
3.2	Elagolix	20
3.2.1	Preclinical Experience	20
3.2.1.1	Toxicology	20
3.2.2	Clinical Experience	20
3.2.3	Pregnancy in Elagolix Studies	27
3.3	Estradiol/Norethindrone Acetate	28
3.4	Differences Statement	28
3.5	Benefits and Risks	29
4.0	Study Objectives	30
5.0	Investigational Plan	30
5.1	Overall Study Design and Plan: Description	30
5.2	Selection of Study Population	40
5.2.1	Inclusion Criteria	41
5.2.2	Exclusion Criteria	43
5.2.3	Prior and Concomitant Therapy	48
5.2.3.1	Prior Hormonal/Anti-Hormonal Medications	49
5.2.3.2	Concomitant Therapy	51
5.2.3.3	Iron Supplementation	51
5.2.3.4	Concomitant Use of Corticosteroids	52
5.2.3.5	Prohibited Therapy	52
5.2.4	Contraception Recommendations	56
5.3	Efficacy, Pharmacokinetic, Biomarker, Optional Exploratory Research Samples and Safety Assessments/Variables	50
5.3.1	Efficacy and Safety Measurements Assessed and Flow Chart	
J.J.1	Littledey and butery wiedsarements Assessed and I low Chart	

5.3.1.1	Study Procedures	60
5.3.1.2	Collection and Handling of Biomarker and Optional Explorator	y
	Research Samples	89
5.3.2	Drug Concentration Measurements	90

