#### **Visit Windows**

Visit windows will be allowed during the Treatment and Post Treatment Follow-Up Periods. Each subsequent visit during the Treatment Period (Months 1 through 48) should be scheduled based on the date of the Day 1 (Randomization) visit.

Specific assessment-related visit windows are allowed. Please refer to Table 1, Visit and Assessment Windows, for assessment-specific visit windows.

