## **COVID-19 Pandemic-Related Acceptable Protocol Modifications**

Due to the COVID-19 pandemic, if the subject is unable to come on-site or to the imaging facility, the DXA and TAU/TVU can be delayed up to 1 month from their scheduled time. Should the delay be longer, AbbVie should be notified.

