### **Bone Mineral Density (DXA Scan)**

DXA scans of the lumber spine, femoral neck and total hip will be performed by qualified technologist/radiologists at the site or affiliated imaging facility utilizing GE Lunar or Hologic equipment and per the acquisition guidelines provided by the Central Imaging Core Lab (central reader). The DXA technologist/radiologist or designee for each investigative site should electronically submit the subject's DXA images to the central reader for review and analysis following acquisition. Subject eligibility and treatment management will be made based on the central reader review. Sites will receive reports from the central reader detailing the results (including T-scores and BMD % change from baseline, as applicable) of the DXA scans performed. Site training and qualifications, including assessment of instruments, will be evaluated/approved by the central reader prior to screening the first subject. Instructions on calibration and standardization of instruments and any additional required information will be specified in a manual from the central reader that will be provided to all study sites. Sites will need to obtain approval from the central reader prior to initiating study scans.

A DXA scan will be performed during Screening Period and sent to the central reader to determine eligibility and serve as the baseline scan for subject management. Subjects with a T-score of < -2.0 at the lumber spine, total hip **or** femoral neck on the screening DXA scan will not be eligible to enter the study.

During the Treatment Period, DXA scans will be performed for all subjects at Months 6, 12, 18, 24, 30, 36, 42 and 48 and will be submitted to the central reader for review and analysis. The central reader will be blinded to the subject's treatment assignment (in the 12-month Treatment Period), but not to the corresponding time point.

[figure not shown]
If the results of any post-baseline DXA prior to and including Month 48, as read by the central reader selected for the study, document a T-score of < -2.5 in the lumbar spine, total hip **or** femoral neck, the subject must be discontinued from study drug dosing and will enter the Follow-Up Period.

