## Year 2, 3 and 4 (Open-Label) Treatment Period

Study drug treatment after Treatment Month 12 will be open-label in which study drug will be dispensed every 3 months (during the on-site visits). The elagolix study drug will be supplied in a carton and the E2/NETA study drug will be supplied in a separate carton.

Study drug will be taken orally twice daily for the entire 48-month Treatment Period. A morning dose of 1 tablet (elagolix or placebo) and 1 capsule (E2/NETA or placebo) and an evening dose of 1 tablet (elagolix or placebo) should be taken each day approximately 12 hours apart. Study drug should be taken with approximately 8 oz. (240 mL) of water

without regard to food. Study drug should be taken at approximately the same time each morning and evening to promote compliance.

If the subject forgets to take the morning dose, she should be instructed to take the morning dose as soon as possible and take the evening dose as scheduled. If the subject forgets to take the evening dose, she should be instructed to take the evening dose as soon as possible; if the subject misses the evening dose completely (until the next morning), the subject should only take the next morning dose.

On days when the subject visits the study site for the scheduled visits, she will take her morning dose at home, prior to the visit. The evening dose will be taken from the newly dispensed supply of study drug. Subjects must return all study drug containers at each scheduled visit.

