# 5.5.3 Method of Assigning Subjects to Treatment Groups

All subjects will be centrally randomized using an IRT. Before the study is initiated, contact information and user guidelines for IRT will be provided to each site. Study drug will be dispensed at the study visits outlined in Appendix C, Study Activities.

As subjects enter into either the Washout Period or the Screening Period, a unique subject number will be assigned to each subject by the IRT. This unique subject number will be used for each subject throughout the study.

After confirming that the subject has met randomization criteria and prior to the Day 1 (randomization) dose, a unique randomization number will be provided via IRT.

Subjects will be randomly assigned by IRT to receive one of the treatment groups as outlined in Section 5.5.1 upon entry into the 12-month Treatment Period. At the Year 1 Treatment Month 12, all subjects will be re-assigned by IRT to receive open label elagolix 300 mg BID plus E2/NETA (estradiol 1.0 mg/norethindrone acetate 0.5 mg QD), including subjects previously randomized to placebo. Subjects re-assigned by IRT will not be assigned new subject numbers.

Study drug must not be dispensed without contacting IRT. Study drug may only be dispensed to subjects enrolled in the study according to kit numbers provided by the IRT.

The randomization schedule will be computer generated by the Statistics Department at AbbVie, North Chicago, IL prior to the start of the study. A copy of all of the randomization schedules will be kept by the Statistics Department at AbbVie and a copy will be forwarded to the IRT provider.

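### For women switching from placebo, a Month 12 DXA taken after the day of the first open-label dose is lost as the BMD baseline, which then falls back to Month 6 or screening

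*SAP*

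**What the plan says.** **Baseline rule.** SAP 9.1: "The baseline during the open-label Treatment Period will be the last non-missing value obtained prior to or on the initiation day" of elagolix plus E2/NETA. For the pooled on-drug set: "The baseline for All Elagolix plus E2/NETA Analysis Set will be the last non-missing value obtained prior to or on the initiation day" of the same treatment. SAP 9.5.2 and its subsections define no baseline specific to BMD, so this general rule governs.

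**Start of open-label drug.** Protocol 5.5.3: "At the Year 1 Treatment Month 12, all subjects will be re-assigned by IRT to receive open label elagolix 300 mg BID plus E2/NETA". Appendix C has open-label kits dispensed at the Month 12 visit. For visit days, Protocol 5.5.1 says: "The evening dose will be taken from the newly dispensed supply of study drug". A switcher's initiation day is therefore her Month 12 visit day.

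**Timing of the scan.** Protocol 5.3.1.1: "DXA scans will be performed for all subjects at Months 6, 12, 18, 24, 30, 36, 42 and 48". No scan is scheduled between Months 6 and 12. Table 1 allows the Month 12 DXA from 15 days before to 4 days after, and on-site visits within ±4 days. Under Visit Windows, each treatment visit "should be scheduled based on the date of the Day 1 (Randomization) visit". The COVID-19 text adds that "the DXA and TAU/TVU can be delayed up to 1 month from their scheduled time". I found no requirement that the Month 12 DXA precede the first open-label dose.

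**Assigning scans to visits.** SAP 9.5.2 refers to an analysis window for scans but gives no limits for it.

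**The concern.** The Month 12 scan is the natural pre-drug reference for a woman leaving placebo. If it is done even one day after the Month 12 visit, it fails the SAP 9.1 cut-off although it complies with the protocol. The rule then reaches back to the previous scan, about six months earlier.

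Two things follow. Placebo time is counted as bone change on elagolix. The change interval also stops matching the exposure interval, because SAP 6.0 starts the All Elagolix duration at the first dose of elagolix plus E2/NETA. The second study objective is the effect of the drug on BMD, so the reference scan for the switch group should not depend on a few days of appointment scheduling.

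A related gap is that the SAP does not say whether such a scan still counts as the Month 12 value in the double-blind comparison with placebo.

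**Working it through.** **Inputs.** Protocol, Definition of Terms: "A month is defined as 28 days". DXA window −15/+4 days and visit window ±4 days (Protocol Table 1). Initiation on the visit day (Protocol 5.5.1 and 5.5.3). A scan on the initiation day still qualifies as baseline (SAP 9.1). I take the DXA window to run from the target day, as visits do.

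**Check of the calendar.** 12 × 28 = 336, 36 × 28 = 1008 and 48 × 28 = 1344 days. These reproduce the top duration categories in SAP 6.0 (≥ 336, ≥ 1008 and ≥ 1344 days).

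**Scan days after initiation.** Allowed Month 12 DXA days: 336 − 15 = 321 to 336 + 4 = 340, which is 20 days. Allowed initiation days: 332 to 340.

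| Month 12 visit | Initiation day | Scan days after initiation | Latest scan after first dose |
|---|---|---|---|
| 4 days early | 332 | 8 of 20 | 8 days |
| on target | 336 | 4 of 20 | 4 days |
| 4 days late | 340 | 0 of 20 | none |

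With a COVID-19 delay of one 28-day month, the scan can be 28 days after initiation for a visit on target, or 28 + 4 = 32 days for a visit 4 days early.

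**Where the baseline goes.** The Month 6 target is 6 × 28 = 168, with DXA days 153 to 172. The Month 6 scan is nominally 336 − 168 = 168 days before initiation (range 332 − 172 = 160 to 340 − 153 = 187).

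**Length of the change interval for an affected woman.**
- Month 18 (day 504): 504 − 168 = 336 days, instead of 504 − 336 = 168. Half is placebo time.
- Month 48 (day 1344): 1344 − 168 = 1176 days, instead of 1344 − 336 = 1008.

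**Possible size, by assumption only.** The documents give no BMD drift on placebo. Assume −1.0 to +0.5% per year. Over 168/365.25 = 0.46 year, an affected woman's change shifts by −0.46 to +0.23 percentage points. If 20% of switchers were affected (illustrative, not an estimate), the group mean would shift by 0.20 × (−0.46) = −0.09 to 0.20 × 0.23 = +0.05 points.

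**Cost of using the late scan instead.** Protocol 3.2.2 reports a mean Month 6 lumbar-spine change of −0.1% (Phase 2b Cohort 1) and −1.1% (Cohort 2) with standard-dose E2/NETA. Assuming linear loss over 168 days:
- 8 days on drug: 0.1 × 8/168 = 0.005 points, or 1.1 × 8/168 = 0.05 points.
- 32 days on drug: 0.1 × 32/168 = 0.02 points, or 1.1 × 32/168 = 0.21 points.

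**The case against.** The best defence is that the problem may rarely occur. The DXA window is lopsided toward early scans, and its +4 days equals the visit window's +4 days. A scan 4 days past target can therefore be on the visit day itself and qualify. A BMD decrease above 8% at Month 12 leads to discontinuation of study drug (Protocol 5.3.1.1), which gives sites a reason to have the result beforehand. All of this stands. It limits frequency but does not close the gap, since nothing requires the earlier scan.

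A second defence is that a baseline should precede drug, which is the convention in Protocol 8.1.5 and SAP 9.1. For scans a few days after the first dose, the arithmetic favours the late scan: about 168 days of placebo time is exchanged for at most 8 days of drug. For COVID-19 delays of about a month, the objection has real weight.

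Some stronger readings are tempting, but the documents do not support them:
- **A fifth of switchers, or 33 of 165 women, are affected.** That needs scan dates spread evenly over the window and every visit on target. It also needs all placebo women to switch, whereas only those completing the first 12 months do. The SAP gives 167 on placebo, against 165 in the protocol. The figure is neither a maximum nor an estimate.
- **The late scan becomes an on-elagolix value.** The SAP does not say so. Without window limits, its assignment is undefined.
- **Individual BMD-decrease categories are materially distorted.** The bounded categories above zero in SAP 9.5.2.1 are 1 to 3 points wide. The documents give no distribution from which to count changes of category.

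**Conclusion.** The gap is real and narrow. Read literally, SAP 9.1 sends the open-label and All Elagolix BMD baseline back to Month 6, or to screening if Month 6 is missing, for any ex-placebo woman scanned after the day of her first open-label dose. Nominally, 168 days of placebo time then enter every later change from baseline.

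How many women are affected cannot be derived from the documents. The effect on group means is likely small, though even that rests on an assumed placebo drift. A reader might infer that the 48-month BMD result is at risk. It is not: only women randomized to elagolix can reach 48 months on drug, and their initiation day is Day 1. The switch group is summarized separately in the open-label period, without tests.

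The conclusion assumes that the SAP's specific open-label rule governs over the general baseline definition in Protocol 8.1.5. That definition refers to initiation of the study drug and is ambiguous for switchers. This is a worthwhile clarification, not a threat to the trial's conclusions.

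**What to change.** Add to SAP 9.5.2: for women randomized to placebo, a Month 12 DXA taken within its Protocol Table 1 window is both the Month 12 double-blind scan and the BMD baseline for the open-label and All Elagolix summaries, even if it falls after the day of the first open-label dose. On the allowed windows, that is at most about 8 days after.

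For Month 12 scans delayed under the COVID-19 provision, run a sensitivity analysis with and without the late scan as baseline.

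The cost is a short addition to the SAP and one sensitivity analysis, with no new data or procedures. The downside is that a few baselines will follow a few days of drug.
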